#### 15.7.5 ENROLLMENT NOTIFICATION TO PROVIDER

Should either Institutional Review Board require it, the following notice will be sent to the participant's provider indicated on the intake form.

Dr. ##### #####  
c/o Clinic  
Street Address 1  
Street Address 2  
City, State Zip

[ DATE ]

RE: Enrollment in Clinical Trial NCT05337306

Dear [ NAME OF CLINICIAN],

I am writing to notify you that your patient, [ PARTICPANT NAME ], has enrolled in a clinical trial managed by GogyUp Inc, the University of Minnesota School of Public Health and the School of Medicine.

Enclosed is the consent form [ PARTICPANT NAME ] completed. Please place this letter and consent form in the patient's medical file.

If you would like to learn more about the study, please visit [gogyup.com/study](http://gogyup.com/study) or contact me directly: [[contact]](mailto:[contact])

Sincerely,

[name]  
Project Principal Investigator  
CEO, GogyUp  
[contact]  
[[contact]](mailto:[contact])

encl.

## 15.8 STEP 8: FOLLOW-UP ASSESSMENT

### Notes:

- If a participant misses a follow-up assessment appointment, make at least three attempts (which can be a mix of voice call / voicemail and SMS messages) to contact and reschedule.
- Participants in the control (non-intervention) group will complete both the HLQ and the Perceived Diabetes Self-Management Scale (PDSMS).
- Participants in the intervention (GogyUp Reader) group will complete the HLQ, PDSMS, and User Experience Questions.

### 15.8.1 1 DAY SMS APPOINTMENT REMINDER - FOLLOW-UP ASSESSMENT

*Hi, this is [your name] – the GogyUp Research Coordinator.*

*I'm looking forward to taking the survey together on [APPOINTMENT DATE AND TIME]. We're planning to meet [ Online / Over the phone ].*

If the participant signed up for an online meeting, text the link. Otherwise confirm you'll call them at this phone number.

*Here is the link for us to meet: [ ZOOM LINK ].*

Record each contact attempt must in the participant's database record.

### 15.8.2 SCRIPT FOR FOLLOW-UP ASSESSMENT - PHONE OR ONLINE MEETING

If the follow-up assessment appointment is schedule as a phone meeting:

*Hello. This is [YOUR NAME] FROM GogyUp. Is [NAME OF PARTICIPANT] available?*

*Wait for confirmation that you are speaking with the participant.*

*I am calling to take our GogyUp / University of Minnesota Type 2 Diabetes survey with you. Is this still a good time?*

*Wait for confirmation that participant is ready, then explain why we're administering the assessment.*

*Great! Before we begin, do you have any questions for me about the survey or the study?*

Answer questions that the participant has, referring to the Online Disclosure Document as necessary.

Display the JotForm assessment.

Administer the HLQ and PDSMS according to directions posted on the JotForm site.

For participants in the intervention group, administer the User Experience Questions after the HLQ and PDSMS. Record participant scores using the online form. If the participant asks additional questions or provides additional feedback, record in the comments area of the participant's database record.

---

#### 15.8.3 MISSED FOLLOW-UP APPOINTMENT SCRIPTS AND PROCEDURE

If a participant misses a follow-up appointment and is unresponsive to three contact attempts (mix of voice mail and SMS messages) sent in intervals of 2 days between messages, then mark the participant as "inactive" and move to enroll another candidate.

If another candidate is identified and attends the follow-up appointment, then mark the inactive candidate as "replaced" in the participant database.

---

##### 15.8.3.1.1.1 VOICEMAIL SCRIPT: MISSED FOLLOW-UP APPOINTMENT

*Hi, this is [YOUR NAME] from GogyUp. I'm calling to leave a message for [NAME OF PARTICIPANT].*

*[NAME OF PARTICIPANT], please call or text me when you have a moment at [\[[contact]\]](#)*

*J. That's [name]*

Record each contact attempt and outcome in the comments area of the participant's database record.

---

#### 15.8.4 SMS SCRIPT: MISSED FOLLOW-UP APPOINTMENT

*Hi [ NAME OF PARTICIPANT ]! This is [ YOUR NAME ] from GogyUp. We were going to meet [ TIME AND DAY OF MEETING ]. When would be a good day and time to reschedule?*

Record each contact attempt and outcome in the comments area of the participant's database record.

## 15.9 BASELINE AND FOLLOW-UP ASSESSMENTS

The majority of the Baseline and Follow-Up Assessments is the 44 question Health Literacy Questionnaire (HLQ) divided into 2 sections. Each assessment will begin with a landing page (sample below) to help orient the participant. Following the landing page, the participant will be presented with each section of the HLQ. The research coordinator will read each HLQ question and record the participant's response.

The Baseline Assessment also has a demographic that serves a few purposes:

- 1) Capture important information that may have dissuaded candidates from initially enrolling (e.g., gender, age, preferred language, etc.) but would allow the team to compare any intervention effect across different sub-groups.
- 2) Pilot a question concerning whether GogyUp impacts a participant's confidence in using a smartphone or tablet to learn new health information.
- 3) In addition to the HLQ, the Follow-Up Assessment includes the Perceived Diabetes Self-Management Scale (PSDMS) and 14 questions to capture end-user Gather information about the user experience for GogyUp's development team (administered to the GogyUp Reader group only).

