# RCT of Assistive-Reading Technology for Post-Visit Type 2 Diabetes Patient Education

Version 1.4

Protocol 1

10 February 2023

Great! Ok – the reason why we’re taking this questionnaire now is to establish every participant’s current understanding of health and diabetes.

Before we begin, do you have any questions for me about the survey or the study?

Answer any questions that the participant has, referring to the Study Disclosure Document as necessary.

Questions that cannot be addressed by the Study Disclosure Document should be forwarded to the Primary Investigators.

If you’re meeting via Zoom, display the JotForm Baseline Assessment form and administer the Health Literacy Questionnaire (HLQ) and Baseline Demographic Questions according to the directions in the JotForm form. Record participant score in the JotForm form. Add any other notable questions asked to the comments area in the participant’s database area.

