## 15.9.4 BASELINE: DEMOGRAPHIC QUESTIONS

1) Birth month and year: \_\_\_\_\_ / \_\_\_\_\_ / \_\_\_\_\_

2) Which gender do you identify with?

- Female
- Male
- Non-binary
- Prefer to self-describe:
- Prefer to not answer.

3) In which country were you born?

\_\_\_\_\_

4) What is your current zip code?

\_\_\_\_\_

5) Which language do you most often use at home?

- English
- Spanish
- Somali
- Hmong
- Vietnamese
- Arabic
- Other (Please specify)

6) How do you most often access the internet?

- Smartphone with a cellular network.
- Smartphone with Wi-Fi
- Tablet with Wi-Fi
- Laptop or desktop with Wi-Fi
- Laptop or desktop and a dial-up telephone line
- Other: (Please specify)
- I don't have access to the internet

7) How confident are you using a smartphone or tablet to learn new information?

- Very confident
- Fairly confident
- Somewhat confident
- Slightly confident
- Not at all confident

8) Please indicate your highest level of education. (Check only **one** box):

- Less than 8 years
- 8 through 11 years
- High school diploma
- GED / Adult Diploma
- 2-year technical degree
- 4-year college degree
- Postgraduate degree (Masters or PhD)

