## 15.9.6 FOLLOW-UP: USER EXPERIENCE QUESTIONS (INTERVENTION GROUP ONLY): LIKERT

1) I am confident using a smartphone or tablet to learn new information.

c Strongly disagree  
c Disagree  
c Neutral  
c Agree  
c Strongly Agree

5) The information on the app is trustworthy.

c Strongly disagree  
c Disagree  
c Neutral  
c Agree  
c Strongly agree

2) The app is easy to use.

c Strongly disagree  
c Disagree  
c Neutral  
c Agree  
c Strongly agree

6) How likely are you to recommend this app to a friend or family member?

c Strongly disagree  
c Disagree  
c Neutral  
c Agree  
c Strongly agree

3) It is easy to navigate within the app.

c Strongly disagree  
c Disagree  
c Neutral  
c Agree  
c Strongly agree

7) I will likely use the app in the future.

c Strongly disagree  
c Disagree  
c Neutral  
c Agree  
c Strongly agree

4) The information on the app is credible.

c Strongly disagree  
c Disagree  
c Neutral  
c Agree  
c Strongly agree

8) I find the app to be attractive.

c Strongly disagree  
c Disagree  
c Neutral  
c Agree  
c Strongly agree

9) The app has a clean and simple presentation.

- c Strongly disagree
- c Disagree
- c Neutral
- c Agree
- c Strongly agree

---

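### The question piloted on whether the app affects device confidence has no like-for-like follow-up, so the planned data allow neither a comparison between arms nor a change within the app arm

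*Combined protocol and SAP*

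**What the plan says.** Section 15.9 lists the purposes of the demographic part of the baseline assessment. The second is to pilot a question on whether the app has an impact on a participant's "confidence in using a smartphone or tablet to learn new health information".

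The baseline item is question 7 in Section 15.9.4: "How confident are you using a smartphone or tablet to learn new information". It has five options, running from very confident down to "Not at all confident". The baseline script in Section 15.6.2 tells the coordinator to "administer the Health Literacy Questionnaire (HLQ) and Baseline Demographic Questions according to the directions in the JotForm form", with no restriction by arm, so both arms answer it.

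At follow-up, a similar statement is item 1 of Section 15.9.6: "I am confident using a smartphone or tablet to learn new information". It has five options from strong disagreement to strong agreement, with a neutral midpoint. The section is headed "FOLLOW-UP: USER EXPERIENCE QUESTIONS (INTERVENTION GROUP ONLY): LIKERT". The notes in Section 15.8 give controls the HLQ and the PDSMS at follow-up, and give the app arm those two instruments plus the user-experience questions. The script in Section 15.8.2 and the text of Section 15.9 agree with this.

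**The concern.** Whether the app affects confidence is a question about the intervention. To answer it, even at pilot level, the same item is needed after the intervention period in both arms, or at the least the same item before and after in the app arm. The plan collects the baseline half in both arms and then changes the stem, the response scale and the set of people asked.

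What is at stake is one stated purpose of one questionnaire item. If the study runs as written, the baseline answers will exist in both arms with nothing comparable to set against them, and no choice of analysis can repair that once follow-up is over.

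**Working it through.** There is no stated figure to reproduce and no sample-size or power calculation involved. The check is a cross-reading of the assessment sections.

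**1. Is there a control follow-up item anywhere?** Controls get the HLQ and PDSMS at follow-up (Section 15.8). The HLQ items in Sections 15.9.2 and 15.9.3 and the PDSMS items in Section 15.9.5 contain no question on device confidence.

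**2. Is the Section 15.9.6 item really part of the app-only block?** Section 15.9 counts 14 user-experience questions, for the app group only. Section 15.9.6 lists 9 Likert items and Section 15.9.7 lists 5 open-ended ones: 9 + 5 = 14. The confidence statement is one of those 14.

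**3. What data result?**

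| | Baseline | Follow-up |
|---|---|---|
| App arm | Question 7, confidence scale | Item 1, agreement scale |
| Control arm | Question 7, confidence scale | Nothing |

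**4. What can be estimated?**
- *Between arms at follow-up:* nothing. The control cell is empty, so neither an unadjusted difference nor a baseline-adjusted one exists.
- *Change within the app arm:* not defined like for like. Both scales have five options, but scoring each from 1 to 5 and subtracting would not help. The middle option at baseline states a moderate amount of confidence; the middle option at follow-up states neither agreement nor disagreement. The plan gives no mapping between them.
- *A same-scale change in the app arm alone*, had it been planned, could still not separate an effect of the app from the passage of time or from being asked twice.

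**5. Could controls answer the item?** Yes. Item 1 is the only one of the nine Likert statements that does not mention the app.

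**6. Does any planned analysis use it?** No. Device confidence is absent from the objectives and endpoints (Section 4), the hypotheses (Sections 5.1 and 10.1), the sample size (Section 10.2) and the primary and secondary analyses (Sections 10.4.2 and 10.4.3). The one exploratory analysis, in Section 10.4.9, relates app use to the primary endpoint.

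**The case against.** The strongest reply is that Section 15.9 speaks of piloting a question, which can mean no more than trying out an item's wording and looking at the spread of answers. The current layout permits that. A reader might infer that the item was meant as a test of a treatment effect; the documents do not support this, since no hypothesis or analysis rests on it. What remains is that the text ties the pilot to whether the app has an impact, and the layout does not try out that use.

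A reader might also infer that Phase II planning would be left without a needed estimate. No section says that Phase II will use a device-confidence estimate. The interim analysis that feeds the application covers the planned endpoints (Section 5.1.3) or the primary endpoints (Section 10.4.6), and Section 3.1 describes Phase II as a trial on health literacy. That inference should not be drawn.

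It can further be said that the user-experience block is product feedback for the developers, for which a common agreement scale is reasonable, and that no section names its first item as the counterpart of baseline question 7. Both are true. But if the two items are not a pair, there is no follow-up item at all for the stated purpose.

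Finally, an adjusted comparison has a weakness of its own. Under the scripts in Sections 15.5.1.1 and 15.5.1.4, assignment is shown to the participant before the baseline survey. The baseline confidence answer is thus a self-report by someone who knows the assigned arm. This objection stands and belongs in any report of the comparison.

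**Conclusion.** The mismatch is real and minor. As written, every control lacks a follow-up answer and no app participant has a like-for-like change, so the data cannot inform whether the app affects device confidence. The conclusion rests on two readings: that the baseline demographic questions go to both arms, since the script sets no restriction, and that Section 15.9.6 is used as headed.

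The primary, secondary and listed exploratory analyses are unaffected. The point is worth acting on because the remedy is small and, without it, Section 15.9 states a purpose that the forms do not serve.

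**What to change.** Ask baseline question 7, with its baseline wording and response options, of both arms at follow-up. Place it after the HLQ and PDSMS so that the endpoint instruments are not disturbed. Let it replace item 1 of Section 15.9.6; the count of user-experience questions in Section 15.9 then becomes 14 − 1 = 13, and the control follow-up content in Sections 15.8 and 15.8.2 gains the item. Report the comparison between arms at follow-up, adjusted for the baseline answer, as exploratory, and state that the baseline answer is given after assignment is disclosed.

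Alternatively, if the sponsor does not want this information, withdraw from Section 15.9 the purpose of learning whether the app has an impact on confidence, and keep the forms as they are.

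The first option costs one extra question for controls, a form edit and IRB approval of the amendment, which Section 1 requires. The second is a change of text only, under the same approval.

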**15.9.1 ASSESSMENT LANDING PAGE**

Both the Baseline and Follow-Up Assessment pages will be as follows:

## GogyUp / U of MN Study

NCT05337306

### Baseline Assessment

Hello !

Thank you for taking the time to complete this questionnaire. We hope the results will help us to improve the way we provide care for our community.

We want to learn about how you find, understand and use health information, and how you manage your health and interact with doctors and other healthcare providers.

In this questionnaire, the term **healthcare providers** means doctors, nurses, physiotherapists, dieticians and any other health worker you seek advice or treatment from.

The following questionnaire contains two parts:

- In Part 1 you are asked to indicate how strongly you disagree or agree with a set of statements.
- In Part 2 you are asked to indicate how difficult or easy you find a set of tasks. For each statement or task check the box that best describes you now.

There are no "correct" answers other than what you select. However, your answers will be very important to our study. Please ensure that you check a box for every statement or task.

All of your responses are confidential.

***Please wait for the research coordinator to say when to click the "BEGIN" button.***

BEGIN

[figure not shown]
Figure 8: Baseline Assessment Landing Page

### 15.9.2 HLQ TEXT – PART ONE

**Part 1 of the questionnaire starts here**

Please indicate how strongly you **disagree** or **agree** with each of the following statements.  
Remember to check only **one** box for each statement.

*Check a box by crossing it like this:*

1	I feel I have good information about health	   
2	I have at least one healthcare provider who knows me well	   
3	I can get access to several people who understand and support me	   
4	I compare health information from different sources	   
5	When I feel ill, the people around me really understand what I am going through	   
6	I spend quite a lot of time actively managing my health	   
7	When I see new information about health, I check up on whether it is true or not	   

**Part 1 continued**

Please indicate how strongly you disagree or agree with each of the following statements. Remember to check only **one** box for each statement.

Strongly disagree  
Disagree  
Agree  
Strongly agree

8	I have at least one healthcare provider I can discuss my health problems with				
9	I make plans for what I need to do to be healthy				
10	I have enough information to help me deal with my health problems				
11	If I need help, I have plenty of people I can rely on				
12	I always compare health information from different sources and decide what is best for me				
13	Despite other things in my life, I make time to be healthy				
14	I am sure I have all the information I need to manage my health effectively				
15	I have at least one person who can come to medical appointments with me				
16	I know how to find out if the health information I receive is right or not				
17	I have the healthcare providers I need to help me work out what I need to do				
18	I set my own goals about health and fitness				
19	I have strong support from family or friends				
20	I ask healthcare providers about the quality of the health information I find				
21	There are things that I do regularly to make myself more healthy				
22	I can rely on at least one healthcare provider				
23	I have all the information I need to look after my health				

## 15.9.3 HLQ TEXT – PART TWO

**Part 2 of the questionnaire starts here**

Please indicate how **difficult** or **easy** the following tasks are for you **now**. Remember to check only **one** box for each statement.

Check a box by crossing it like this: 

Cannot do or always difficult  
Usually difficult  
Sometimes difficult  
Usually easy  
Always easy

1	Find the right health care	    
2	Make sure that healthcare providers understand your problems properly	    
3	Find information about health problems	    
4	Feel able to discuss your health concerns with a healthcare provider	    
5	Confidently fill medical forms in the correct way	    
6	Find health information from several different places	    
7	Have good discussions about your health with doctors	    
8	Get to see the healthcare providers you need to	    
9	Accurately follow instructions from healthcare providers	    
10	Get information about health so you are up to date with the best information	    
11	Decide which healthcare provider you need to see	    
12	Read and understand written health information	    
13	Make sure you find the right place to get the health care you need	    

**Part 2** continued

Please indicate how **difficult** or **easy** the following tasks are for you now. Remember to check only **one** box for each statement.

Cannot do or always difficult  
Usually difficult  
Sometimes difficult  
Usually easy  
Always easy

14	Get health information in words you understand	    
15	Discuss things with healthcare providers until you understand all you need to	    
16	Find out which healthcare services you are entitled to	    
17	Read and understand all the information on medication labels	    
18	Get health information by yourself	    
19	Work out what the best care is for you	    
20	Ask healthcare providers questions to get the health information you need	    
21	Understand what healthcare providers are asking you to do	    

## 15.9.4 BASELINE: DEMOGRAPHIC QUESTIONS

1) Birth month and year: \_\_\_\_\_ / \_\_\_\_\_ / \_\_\_\_\_

2) Which gender do you identify with?

- Female
- Male
- Non-binary
- Prefer to self-describe:
- Prefer to not answer.

3) In which country were you born?

\_\_\_\_\_

4) What is your current zip code?

\_\_\_\_\_

5) Which language do you most often use at home?

- English
- Spanish
- Somali
- Hmong
- Vietnamese
- Arabic
- Other (Please specify)

6) How do you most often access the internet?

- Smartphone with a cellular network.
- Smartphone with Wi-Fi
- Tablet with Wi-Fi
- Laptop or desktop with Wi-Fi
- Laptop or desktop and a dial-up telephone line
- Other: (Please specify)
- I don't have access to the internet

7) How confident are you using a smartphone or tablet to learn new information?

- Very confident
- Fairly confident
- Somewhat confident
- Slightly confident
- Not at all confident

8) Please indicate your highest level of education. (Check only **one** box):

- Less than 8 years
- 8 through 11 years
- High school diploma
- GED / Adult Diploma
- 2-year technical degree
- 4-year college degree
- Postgraduate degree (Masters or PhD)

## 15.9.5 FOLLOW-UP: PERCEIVED DIABETES SELF-MANAGEMENT SCALE (PSDMS)

INSTRUCTIONS: This is a questionnaire designed to determine how well you, yourself, feel you manage your diabetes. Each item is a belief statement with which you may agree or disagree. Next to each statement is a scale which ranges from strongly disagree to strongly agree. Please respond to each of the following items by choosing one number for each statement. Try to respond to each statement separately in your mind from each other statement. Choose your responses thoughtfully and make them as true FOR YOU as you can. Please respond to every statement.

1. It is difficult for me to find effective solutions for problems that occur with managing my diabetes.
  - c Strongly disagree
  - c Disagree
  - c Neutral
  - c Agree
  - c Strongly agree
2. It is difficult for me to find effective solutions for problems that occur with managing my diabetes.
  - c Strongly disagree
  - c Disagree
  - c Neutral
  - c Agree
  - c Strongly agree
3. I handle myself well with respect to my diabetes.
  - c Strongly disagree
  - c Disagree
  - c Neutral
  - c Agree
  - c Strongly agree
4. I am able to manage things related to my diabetes as well as most other people.
  - c Strongly disagree
  - c Disagree
  - c Neutral
  - c Agree
  - c Strongly agree
5. I succeed in the projects I undertake to manage my diabetes.
  - c Strongly disagree
  - c Disagree
  - c Neutral
  - c Agree
  - c Strongly agree
6. Typically, my plans for managing my diabetes don't work out well.
  - c Strongly disagree
  - c Disagree
  - c Neutral
  - c Agree
  - c Strongly agree

RCT of Assistive-Reading Technology for Post-Visit Type 2 Diabetes Patient Education

Version 1.4

Protocol 1

10 February 2023

7. No matter how hard I try, managing my diabetes doesn't turn out the way I would like.

c Strongly disagree

c Disagree

c Neutral

c Agree

c Strongly agree

8. I'm generally able to accomplish my goals with respect to managing my diabetes.

c Strongly disagree

c Disagree

c Neutral

c Agree

c Strongly agree

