## 4 OBJECTIVES AND ENDPOINTS

OBJECTIVES		ENDPOINTS	JUSTIFICATION FOR ENDPOINTS	PUTATIVE MECHANISMS OF ACTION
P r i m a ry	The primary objective of this study is to conduct a pilot trial of the effect of the GogyUp Reader app on health literacy.	The primary endpoint are the three-month (follow up) values of two validated subscales of the Health Literacy Questionnaire: Understanding health information well enough to know what to do (“Understanding health information”); and having sufficient information to manage my health (“Having sufficient information”)..	This study’s main objective is to study the effect of GogyUp on aspects of health literacy that relate the ability to understand and use written health information as the most proximal effect of in-the-moment support. As such, these two subscales are the most direct measures; the three-month time frame reflects (a) a brief follow-up as part of a pilot trial; and (b) is reasonable because of the use of this proximal outcome based on putative mechanisms.	The mechanism of action is a chain whereby improved in-the-moment capacity to interact with print patient education materials and care instructions improves the ability to use and understand written health information.
S e c o n d a ry	The secondary objectives are to assess the effect of GogyUp Reader on participants’ ability to self-manage their diabetes.	The secondary endpoint is the three-month (follow up) value of the Perceived Diabetes Self-Management Scale (PDSMS)..	The PDSMS and self-management generally are less proximal to the intervention but reflect a more pragmatic outcome further along the causal chain toward actually affecting health outcomes.	Health literacy (primary outcomes) is a foundational hurdle to understanding self-management needs and expectations. While our focus is that most proximal outcome focused on ability to use/understand written materials (primary endpoints), this secondary endpoint will indicate whether GogyUp Reader has effects that are closer to actually impacting outcomes (i.e., health literacy and understanding may or may not lead to improved self-management activities to better control diabetes).

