## 5 STUDY DESIGN

### 5.1 OVERALL DESIGN

#### Hypotheses:

H1: GogyUp Reader app use with written patient education materials or self-care instructions will result in better health literacy in understanding health information compared with print patient education or care plan materials alone.

H2: GogyUp Reader app use with written patient education materials or self-care instructions will result in better health literacy in reporting having enough information compared with print patient education or care plan materials alone.

H3: GogyUp Reader app use with written patient education materials or self-care instructions will result in better diabetes self-management compared with print patient education or care plan materials alone.

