### 10.2 SAMPLE SIZE DETERMINATION

Due to lack of literature on meaningful effect size for our primary effectiveness outcome, our power calculation is based on a general effect size, the standardized mean difference (SMD). SMD consists of the mean difference in the outcome between arms, divided by the standard deviation of the outcome in the control arm, with moderate effect size being SMD=0.5 and large effect size being SMD=0.7. Based on information in the original validation paper, mean Understanding subscale summary score was 3.85, standard deviation 0.74. With 60 subjects per arm (a low estimate), we will have 78% power to detect a moderate effect size (a between-group difference of .37 on the scale, SMD=0.5) and 97% power to detect a large effect size (SMD=0.7, difference of .52) based on performing a two-sample t-test comparing the treatment arms. With differences in post means of 0.3 and 0.5, power will be 60% and 96%, respectively. However, we want to help insure against difficult recruitment as well as, in particular, a potentially smaller effect size, which can have a large impact on sufficient power. Therefore, our targeted enrollment is 80 per arm (n=160), which would support 73% power for a .3 difference in post means (modest of SMD of .405), with attempted recruitment of up to 200 (given a possible 20 percent recruitment/screening failure rate). Individuals who withdraw or otherwise lost to follow-up will be included in the analysis (see below re: attrition). Regarding our other primary endpoint, for the having sufficient information subscale, (mean 2.98, standard deviation .54), 80 participants per arm would provide 72% power to detect a modest SMD of .40 and 60 participants would provide 78% power to detect a SMD of .5. For our secondary outcome, the perceived diabetes self-management scale (mean 2.585, standard deviation .455), 80 participants per arm would provide 72% power to detect SMD=.4, and 60 participants would likewise provide .78 power to detect SMD=.5.

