#### 10.4.3 ANALYSIS OF THE SECONDARY ENDPOINT(S)

The secondary endpoint will be analyzed and presented in the same manner as the primary endpoint, with the same model assumptions and the same approach to missing data. The analysis will not depend on findings or analysis of the primary endpoint.

The secondary endpoint, like the primary endpoints, is a continuous score.

---

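### The PDSMS form in section 15.9.5 prints one statement as both item 1 and item 2, leaving seven distinct statements in eight slots for the only secondary endpoint

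*Combined protocol and SAP*

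**What the plan says.** Sections 2.1 and 4 make the three-month PDSMS value the only secondary endpoint. It is the measure for H3 in section 5.1, that the app "will result in better diabetes self-management compared with print patient education or care plan materials alone".

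Section 15.9.5 prints the form. Items 1 and 2 both read "It is difficult for me to find effective solutions for problems that occur with managing my diabetes". Each has its own number and its own full set of five responses, and items 3 to 8 follow in order. The instructions above the items ask participants: "Try to respond to each statement separately in your mind from each other statement".

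On scoring, section 10.4.3 says only this: "The secondary endpoint, like the primary endpoints, is a continuous score". Section 10 adds that the protocol holds all the statistical detail and that there is no separate analysis plan. Section 10.2 quotes a mean of 2.585 and an SD of 0.455 for the scale. It gives power of 72% for a standardised mean difference (SMD) of 0.4 with 80 per arm, and 78% for an SMD of 0.5 with 60 per arm.

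Section 15.8 has both arms complete the PDSMS at follow-up. Section 15.8.2 tells staff: "Administer the HLQ and PDSMS according to directions posted on the JotForm site". The live PDSMS form is not reproduced.

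**The concern.** Two identical statements cannot sensibly be answered separately from each other, so the printed form looks like a copying slip. If it was fielded as printed, staff ask one statement twice in both arms. If a different statement belongs in that slot, it is never asked, and an answer that was not collected cannot be recovered later.

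Nothing else in the protocol protects the score. No section lists the PDSMS items elsewhere, says how many there should be, or says whether they are summed or averaged. None says which items are reverse-coded, although slots 1, 2, 6 and 7 are worded negatively and slots 3, 4, 5 and 8 positively. A default score over all eight slots would count the repeated statement twice.

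Sections 3.1 and 3.2 say the pilot is meant to supply data for a larger Phase II trial. A score whose content differs from the cited scale is a weak basis for carrying a PDSMS effect or SD into that design.

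**Working it through.** **Item count (section 15.9.5).** There are eight numbered slots, ending with item 8, "I'm generally able to accomplish my goals with respect to managing my diabetes". Slots 1 and 2 match word for word and no other pair does. Distinct statements: 8 − 1 = 7. Separate numbers and separate response sets make a PDF-reading fault unlikely.

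**Weight, if all eight slots are scored equally.** Eight different statements carry 1/8 = 12.5% each. As printed, the repeated statement carries 2/8 = 25% and each of the other six carries 12.5%.

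**The plan's own power figures (section 10.2).** Inputs are two-sided alpha 0.05 (section 10.4.1) and 1:1 allocation (section 5.1.3). In the normal approximation, power = Φ(SMD × √(n/2) − 1.96).

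- n = 80 per arm, SMD 0.4: 0.4 × √40 − 1.96 = 0.570, giving 71.6% (noncentral t 71.0%; stated 72%).
- n = 60 per arm, SMD 0.5: 0.5 × √30 − 1.96 = 0.779, giving 78.2% (noncentral t 77.5%; stated 78%).

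Both reproduce. They are set in SMD units, so they do not depend on the quoted mean and SD.

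**Illustrative effect of the repeat on power.** The documents give no item-level data. Assume equal item SDs, equal item effects, a common inter-item correlation r between 0.2 and 0.6, and identical answers to the two copies. With item variance set to 1, the variance of the mean score is:

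- eight distinct items: V8 = (1 − r)/8 + r
- seven distinct items, one counted twice: V7 = (1 − r) × 10/64 + r, since the squared weights sum to (2² + 6 × 1²)/64 = 10/64

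The mean shift is the same in both cases, so the SMD is multiplied by √(V8/V7). Power below is from the noncentral t.

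| r | V8 | V7 | SMD factor | Power, n = 80, SMD 0.4 | Power, n = 60, SMD 0.5 |
|---|---|---|---|---|---|
| no repeat | – | – | 1 | 71.0% | 77.5% |
| 0.2 | 0.300 | 0.325 | 0.961 | 67.6% | 74.2% |
| 0.4 | 0.475 | 0.494 | 0.981 | 69.4% | 75.9% |
| 0.6 | 0.650 | 0.663 | 0.991 | 70.2% | 76.8% |

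The loss is about 1 to 3.5 percentage points.

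**The case against.** The strongest reply is that section 15.9.5 may not be what participants see. Staff work from the live JotForm, which the documents do not show, and the slip may exist only in the protocol's transcription. This stands. It makes checking the live form the first step, and it means that nothing shows any participant was affected.

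A reader might also infer that an item of the published scale was overwritten, and that H3 is therefore not tested with the scale the protocol names. The documents do not support going that far. They cite the source paper but do not reproduce its items or state how many there are. Eight numbered slots with a repeat make a lost item plausible, but do not prove it. The 25% weight is conditional too, because no scoring rule is given. Nor do the documents show whether slot 1 or slot 2 is the wrong one.

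Third, the consequences are limited. Both arms complete the same form, so the repeat neither biases the randomised comparison nor inflates its type I error. The primary endpoints, Health Literacy Questionnaire subscales 9 and 2, are untouched. This is a secondary endpoint in a pilot, and the illustrated power loss is small. All of that stands. It does not answer the loss of content and comparability, or the missing scoring rule.

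**Conclusion.** The point holds in a limited form. It is certain that the current text (Version 1.4) prints one statement twice on the form for the only secondary endpoint, leaving seven distinct statements, and that no other section corrects this or gives a scoring rule.

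Two conditions govern the rest: that the live form matches the printed one, and that all eight slots are scored equally. If both hold, one statement has double weight, and the score may not match the cited scale or the mean and SD in section 10.2. H3 would still be tested by a fair between-arm comparison, but on a score with altered content. The cost falls mainly on content coverage and on use of the result in planning the next trial; the power figures rest on the assumed correlations.

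It deserves action before more data are collected because an unasked item cannot be recovered and the check costs almost nothing.

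**What to change.** 1. Before further PDSMS administration, compare the live JotForm and section 15.9.5 item by item with the source instrument, and correct whichever of slots 1 and 2 is wrong.
2. State the scoring rule in section 10.4.3: the items used, sum or mean, response coding, and reverse-coding of the negatively worded items.
3. If anyone was assessed on a duplicated form, flag those records and count the repeated statement once. Fix in advance which answer is kept when the two differ (for example, the first) and how a seven-statement record is put on the same metric as a complete one. Report H3 with and without the flagged records.

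The cost is a minor form amendment and, only if a duplicated form was used, one extra sensitivity analysis. Participants face no added burden if a repeated question is replaced by a different one.
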